1.2 Secondary Objectives

- 1.2.1 To measure the breast tissue concentrations of (E) and (Z) isomers of N- desmethyl-4-hydroxytamoxifen (ENX) and 4-hydroxytamoxifen (4-OHT) at each dose (10 mg per day and 20 mg per day).
- 1.2.2 To measure the plasma concentrations of (E) and (Z) isomers ENX and 4-OHT at each dose (10 mg per day and 20 mg per day).
- 1.2.3 To measure plasma hormone levels for steroid hormones (estradiol, progesterone, dehydroepiandrostenedione [DHEA], androstenedione, testosterone) in comparison to vehicle placebo gel.
- 1.2.4 To measure serum estrogenic response to topical ENX gel therapy in comparison to vehicle placebo gel (sex hormone binding globulin and IGF pathway proteins).
- 1.2.5 To assess changes in coagulation parameters (Factor VIII, Factor IX, vWF, Protein S) in response to ENX gel therapy in comparison to vehicle placebo gel.
- 1.2.6 Using pre- and post-therapy tissue samples, to explore the potential therapeutic effects of the two doses of ENX gel in comparison to vehicle placebo gel: a) by IHC, Ki67 labelling (for cell proliferation), estrogen receptor (ER), progesterone receptor (PR) expression (for estrogen blockade); b) by expression of a panel of genes reported to change with ENX exposure (using nanostring assays).
- 1.2.7 Bank germline DNA for future pooled analyses of polymorphisms in tamoxifen metabolizing enzymes in comparison to vehicle placebo gel (optional).
- 1.2.8 To assess symptoms related to use of endoxifen gel in comparison to vehicle placebo gel, as assessed by the Breast Cancer Prevention Trial (BCPT) Eight Symptom Scale (BESS) questionnaire.

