2.3 Rationale

2.3.1 Hypotheses

Our *primary hypothesis* is that ENX gel at 20 mg daily (10 mg per breast) will be safe and tolerable as assessed objectively using CTCAE criteria, in comparison to the placebo group.

Our secondary hypotheses include 1) the breast tissue concentrations of ENX at will reach the concentrations achieved in our prior study of oral tamoxifen versus 4-OHT gel (5.8 ng/g tissue) [36]. 2) The plasma concentrations of ENX at each dose (10 mg per day and 20 mg per day) will be significantly lower than those seen in women on oral tamoxifen. 3) Plasma hormones (estradiol, progesterone, DHEA, androstenedione, testosterone) will not be changed by ENX gel use. 4) Changes in serum estrogenicity (sex hormone binding globulin and IGF pathway proteins) will be minimal, if any. 5) Changes in coagulation parameters (Factor V, Factor VIII, von Willebrand factor, Protein S) will be minimal, if any. 6) Biologic endpoints such as Ki67 labeling index, ER, and PR expression, and expression of a panel of genes reported to change with ENX exposure, will be consistent with a therapeutic effect of ENX gel. 7) Polymorphisms in tamoxifen metabolizing enzymes will not affect breast tissue ENX concentration. This hypothesis will not be tested in the current study, but germline DNA will be banked for future pooled analyses of transdermally versus orally administered tamoxifen and metabolites relative to metabolic efficiency for oral tamoxifen. Banking of germline DNA for future pooled analyses will be optional for participants. 8) Symptoms reported with the use of ENX gel will be similar between treated and placebo groups.

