13.5 Secondary Objectives, Endpoints, Analysis Plans

Secondary objectives:

- 1) Comparison of breast tissue concentrations of ENX at each dose will be done using visualization, graphics and by providing appropriate confidence interval (CI).
- 2) Plasma concentrations of ENX at each dose (10 mg per day and 20 mg per day), will be reported as observed concentrations with appropriate CIs.
- 3-5) Relate to comparison of the plasma levels for steroid hormones, plasma estrogenic response proteins, and plasma coagulation parameters. To assess treatment-related changes, the 95%CI of the mean difference post-pre and a test of the central parameter = 0 will be provided as in the previous objective.
- 6) To assess tissue biologic response to ENX gel treatment. These will be compared as pre- and post-therapy values, to explore the potential therapeutic effects of the two doses of ENX: a) by IHC for Ki67, ER, and PR expression; b) by nanostring assays, using a panel of genes reported to change with ENX exposure. For both IHC and gene expression, values for "pre" and for "post" measurements will be subtracted from each other and CIs for the mean difference will be provided. A nonparametric test of the central parameter being zero will be performed.
- 7) To bank germline DNA for future pooled analyses of polymorphisms in tamoxifen metabolizing enzymes, statistical analysis will be used as needed (optional).
- 8) Analysis of symptoms as reported in the BESS questionnaire: This uses scores where the lowest describes "no symptom" and the highest reflects "extremely" or "always". The high scores are adverse. When subtracting post-pre measures, negative values suggest improvement over time, while positive suggest worsening. We will provide graphical displays of these differences as histograms with x-axis values -5, -4, ...0, ... 4, 5 and empirical mass function on the top. To compare the dose groups (low, high) and singular dose versus placebo, if appropriate, we will use the nonparametric two sample Wilcoxon-Mann-Whitney test, with corrections for ties. The study was not specifically powered for such analysis, and resulting one and two sided p-values will be considered descriptive statistics useful for future analyses. Average, median and range of scores for each noted group will be provided as descriptive measures of location and variance. We will use multiple imputation via non-parametric probability integral transformation[53] to impute missing data as appropriate.

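### Hypotheses 3–5 predict no or minimal change, but 13.5 sets no range for minimal, so a non-significant test of zero cannot support them

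*Combined protocol and SAP*

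**What the plan says.** Section 2.3.1 gives three secondary hypotheses that predict little or no systemic effect:

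- Hypothesis 3: "Plasma hormones (estradiol, progesterone, DHEA, androstenedione, testosterone) will not be changed by ENX gel use".
- Hypothesis 4: "Changes in serum estrogenicity (sex hormone binding globulin and IGF pathway proteins) will be minimal, if any".
- Hypothesis 5: "Changes in coagulation parameters (Factor V, Factor VIII, von Willebrand factor, Protein S) will be minimal, if any".

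Section 13.5 items 3–5 give the matching analysis in one sentence: "the 95%CI of the mean difference post-pre and a test of the central parameter = 0 will be provided". It contains an interval estimate and a test. The test is not named, no significance level or SD of change is given, and no numerical range defines a minimal change.

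Objectives 1.2.3 to 1.2.5 ask for these markers to be compared with vehicle placebo. Items 3–5 describe only the change from before to after treatment.

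On numbers, Section 3.2.1 reports eight women on active gel and four on placebo in each of Cohorts 1 (10 mg) and 2 (20 mg). Cohort 3 adds eight women on active gel at 10 mg. Section 13.1 pools placebo to n=8 and accepts that formal comparison is limited by the small sample.

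**The concern.** In items 3–5 the null value of the test is the state of affairs that the hypotheses predict. Rejecting it would count against a hypothesis. Failing to reject it is what a small sample tends to produce, whether or not a change exists. A confidence interval could settle the matter by showing which changes are excluded, but only if the plan says which changes matter.

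What is at stake is the systemic-safety argument. Sections 2.1 and 2.2 rest the case for treating through the breast skin largely on low systemic exposure. A report of no significant change in clotting proteins or SHBG could be carried into later trials as reassurance, although the data might be compatible with a change worth knowing about.

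**Working it through.** **Inputs from the documents.** Active n = 8 at 20 mg. Active n = 8 at 10 mg in Cohort 1, or 8 + 8 = 16 with Cohort 3. Placebo n = 4 + 4 = 8. Interval level 95%; tests two-sided (Section 13.5).

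**Assumptions.** Alpha is taken as 0.05. Results are in units of the SD of the within-woman change because the documents give no SD. Changes are taken as roughly normal.

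**The plan's own precision figure.** Section 13.1 gives a standard error of SD/√8 for pooled placebo. 1/√8 = 0.354, so the SE is 0.354 SD. This reproduces. No power or margin is stated for hypotheses 3–5, so there is nothing further to reproduce.

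**Step 1: 95% CI half-width, t(0.975, n−1)/√n.**

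- n=8: 2.365/2.828 = 0.84 SD.
- n=16: 2.131/4 = 0.53 SD.

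A 20 mg group with an observed mean change of exactly zero would still have an interval reaching 0.84 SD in each direction.

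**Step 2: power of the one-sample t-test (noncentral t, noncentrality d√n).**

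| True mean change d | n=8 | n=16 |
|---|---|---|
| 0.5 SD | 23% | 46% |
| 0.8 SD | 50% | 85% |
| 1.0 SD | 68% | 96% |
| d for 80% power | 1.16 SD | 0.75 SD |

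By simulation, a signed-rank test has slightly less power at n=8: 19%, 43% and 61%.

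**Step 3: illustration on the ratio scale.** Suppose a protein truly rises by 25%, so the log change is ln(1.25) = 0.223. With an assumed within-woman log-SD of 0.2, 0.3 or 0.4, d = 1.12, 0.74 or 0.56. The t-test misses the change with these probabilities:

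- n=8: 23%, 56%, 72%.
- n=16: 1%, 21%, 45%.

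**Step 4: what a range-based rule could show.** Take 0.80–1.25 as an illustrative range (±0.223 on the log scale) and a 90% CI. The half-width factor t(0.95, n−1)/√n is 1.895/2.828 = 0.670 at n=8 and 1.753/4 = 0.438 at n=16. An estimate centred exactly on no change fits inside only if the log-SD is at most:

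- n=8: 0.223/0.670 = 0.33.
- n=16: 0.223/0.438 = 0.51.

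With the plan's 95% interval the limits are 0.223/0.836 = 0.27 and 0.223/0.533 = 0.42.

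Real estimates are not perfectly centred. With a true change of zero, simulation puts the chance that the 90% CI falls inside the range at n=8 at 77%, 27% and 7% for log-SD 0.2, 0.3 and 0.4. At log-SD 0.33 it is about 18%.

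**Step 5: precision against placebo.** The 95% half-width for a difference in mean change, t(0.975, n₁+n₂−2)·√(1/n₁+1/n₂), is 2.145 × 0.5 = 1.07 SD for 8 against 8 and 2.074 × 0.433 = 0.90 SD for 16 against 8. The placebo contrast is wider still, so it can give context but will seldom settle a hypothesis.

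**The case against.** The strongest reply is that the plan is not a bare significance test. The sentence in items 3–5 puts the 95% CI before the test, and Section 13.8 promises 95% intervals for all measurements of response. The objectives are to measure and assess, as in any Phase I trial, and no trial decision depends on these markers. This stands. The interval is the right tool, and what is missing is a range to judge it against.

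A reader might infer that the sponsor means to declare the markers unchanged when the test is non-significant. No section says so, and Section 13.1 warns that formal comparison is limited. The supported point is that the plan leaves this reading open and offers no other criterion.

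A reader might also extend the criticism to hypothesis 8 on symptoms ("Symptoms reported with the use of ENX gel will be similar between treated and placebo groups"). The documents do not support that equally. For item 8, "we will use the nonparametric two sample Wilcoxon-Mann-Whitney test, with corrections for ties". That compares groups, as the hypothesis does; the lack of power is stated, and "resulting one and two sided p-values will be considered descriptive statistics useful for future analyses". Items 3–5 carry no caveat of that kind.

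It can fairly be said that eight per dose understates the 10 mg group. If Cohorts 1 and 3 are pooled, n is 16 and the problem shrinks considerably. Section 13.2 refers to analysis by dose, though for efficacy, and no section confirms pooling for these markers.

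Finally, a range-based rule will often fail at n=8 even when nothing changes (Step 4). This is true. It reflects what eight women can show and is not a reason to rely on the test of zero.

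**Conclusion.** The point holds for hypotheses 3–5. Without a stated range, neither output in items 3–5 can confirm that a change is absent or minimal, and a non-significant test is weak evidence. At 20 mg, changes of up to 0.84 SD around the estimate remain compatible with the data, and 80% power needs 1.16 SD. At 10 mg with pooling the figures are 0.53 SD and 0.75 SD.

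The SD-unit results rest on alpha 0.05, approximate normality and complete data. Exclusion of non-compliant women under Section 8.3 would widen the intervals. The ratio-scale examples also rest on assumed log-SDs and an illustrative range.

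These are secondary endpoints and no dose or stopping decision depends on them. The point is worth correcting because it governs what may be concluded about systemic effect; it does not undermine the trial.

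**What to change.** In Section 13.5 items 3–5:

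1. State that the test of zero is not evidence for hypotheses 3–5.
2. Analyse each analyte as a log post/pre ratio with its CI, by dose, and say whether Cohorts 1 and 3 are pooled at 10 mg.
3. Show the placebo change, with its CI, beside each dose, because objectives 1.2.3 to 1.2.5 call for that comparison. Note that Cohort 3 is not randomised.
4. Fix a no-relevant-change range and CI level per analyte, on the laboratory's advice, before these marker data are examined. The range 0.80–1.25 is only an example. Conclude unchanged or minimal only if the CI lies wholly inside the range; otherwise report inconclusive.
5. If ranges cannot be agreed, or the markers have already been examined, report items 3–5 as estimation only and make no claim of no change. Section 3.2.1 describes an interim analysis after Cohort 2 but does not say whether these markers were included.

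No new data are needed. The cost is the effort of agreeing ranges for 12 analytes (5 hormones, 3 SHBG/IGF proteins, 4 clotting proteins) and accepting that many, especially the more variable ones, will be inconclusive at n=8.

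As a separate editorial item, hypothesis 5 names Factor V, whereas objective 1.2.5 reads "To assess changes in coagulation parameters (Factor VIII, Factor IX, vWF, Protein S" and Sections 8.2, 9.1 and 10.1.2 also list Factor IX. Correct Factor V to Factor IX in hypothesis 5.

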Transdermal dose selection: Our in vitro (human skin)[21] and in vivo (rodent) data[17] demonstrates that ENX in a 60% (v/v) alcoholic gel with 0.5%(v/v) oleic acid, penetrates well and concentrates best in the mammary gland to which it is applied. (Z) ENX citrate salt (>97%) from Jina Pharmaceuticals [32, 33] was used for our in vivo animal study. Briefly, in a non-GLP (Good Laboratory Practice) study, we randomized nude rats into four groups: no treatment, oral TAM (3 mg/kg/day), 4-OHT gel (1 mg/kg/day), ENX gel (1 mg/kg/day), and treated them daily. There were no deaths, no weight loss, and no skin irritation at the end of the experiment. Gjerde et al. have reported dose-dependent increases in concentrations of ENX following administration of oral TAM, [34]. ENX concentration in normal breast tissue was not determined; however, it is safe to assume that these too will rise with increasing oral (and transdermal) dose. Our results from a pre-surgical phase IIb trial of transdermal 4-Hydroxytamoxifen versus oral tamoxifen in women with DCIS of the breast (NWU07-9-02) showed that women taking oral TAM 20 mg/day for at least 6 weeks achieved median ENX concentration of 8 ng/g in mammary adipose tissue [16]. Our preclinical data showed that daily oral TAM (3 mg/kg/day) for 6 weeks achieved the mammary concentration of 4-OHT and ENX of median 4~5 ng/g each in rats [17]. Plasma ENX concentration of women treated with 20 mg dose of oral TAM daily (NWU07-9-02) was 6 ng/mL (16 nM) [16]. Plasma ENX concentration of oral TAM-treated rats (3 mg/kg/day dose) was 3 ng/mL (8 nM), but 1.8 ng/mL (5 nM) in ENX-gel treated rats (1 mg/kg/day dose) [17]. The human equivalent dose (HED) of 3 mg/kg/day of oral TAM in rats is 0.48 mg/kg/day or 28.8 mg/day per 60 kg women and the HED of 1 mg/kg/day of 4-OHT or ENX gel in rats is 0.16 mg/kg/day or 10 mg/day per 60 kg women. PK-PD modeling by Gong et al. shows tumor growth inhibition (TGI) in dose-ranging experiments of oral (Z) ENX in MCF7 xenograft bearing mice [35]. Therefore, our and others preclinical data suggest that our rat dose of (Z) ENX 1 mg/kg/day (HED 0.16 mg/kg/day or 10 mg/day per 60 kg women) is in the efficacious range, and given the expected high mammary concentrations, could potentially be lowered to reach the minimal effective dose.

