- 3.5.2 Baseline and end-of-intervention photos and skin toxicity assessment using CTCAE criteria. The photographs will be taken by the coordinator as a standardized single frontal view of both breasts (the view will include from the bottom of the neck to below the breasts, and from the lateral side of one breast to the lateral side of the other breast), and side views of each breast. They will be uploaded to NOTIS and viewed by [name] for scoring.

3.6 *Measurements taken to meet secondary study objectives*

Screening Visit 1: At entry for consent, review of eligibility, instructions on how to apply study agent, baseline symptom assessment, concomitant medication review, blood draw for clinical and research labs, urine or serum pregnancy test in women of child bearing potential, last menstrual period, BESS questionnaire, breast skin photos, CTCAE criteria assessment, and dispensing study agent.

Study Visit 1: Day before surgery. Symptom and adverse event assessment, concomitant medication review, last menstrual period, BESS questionnaire, breast skin photos, CTCAE criteria assessment, and study agent compliance.

Study Visit 2: Day of surgery. Blood draw for clinical and research labs, urine or serum pregnancy test in women of child bearing potential, physical exam, medical history, and tissue for research. Study visit 1 and 2 may be combined on day of surgery.

Study Visit 3: Post-operative visit. Symptom and adverse event assessment, concomitant medication review, last menstrual period, breast skin photos, and CTCAE criteria assessment.

- 3.7 Clinical procedures, lab tests and other measurements taken to monitor effects and safety of study agent.
 - Skin evaluation through history, physical examination (documented by skin photographs and CTCAE criteria). This will be performed at study entry and at the end of intervention.
 - Clinical blood tests pre and post intervention to establish good hematologic, renal, and liver function.
 - Research blood tests pre and post intervention to evaluate effects on coagulation pathway proteins and markers of systemic estrogenicity.
 - Urine pregnancy test in women with childbearing potential (pre and post intervention)
 - Breast size and body mass index (BMI) pre intervention.
 - Examination of breast tissue and plasma samples for drug concentration (at the end of intervention) and antiestrogenic effects of ENX gel (comparing samples obtained prior to and following intervention).

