8.2 Secondary Endpoints

Demonstrate dermal permeation of ENX gel is similar to ENX levels achieved with oral delivery (mean values of 5-6 ng/G breast tissue). The mastectomy will be bread-sliced as per usual pathology protocol. Drug concentration in non-tumor tissues will be measured at 5 different sites within each breast. The central slice (in line with the nipple, will be sampled as shown in Figure 2 Two additional slices will be sampled, half-way between the center and the periphery of the breast, medially and laterally. The mastectomy specimen will be collected at surgery; the PCF will be called by the OR nurse as soon as the specimen is removed; details are described in section 10.2.2. If skin is resected (i.e. if the procedure is not a nipple-sparing mastectomy), a skin sample will also be collected for dermatological pathology assessment. The drug assays will be performed by LC/MS-MS as in our previous study [36].

- 2. Plasma concentration of drug: (E) and (Z) isomers of N- desmethyl-4-hydroxytamoxifen (ENX) and 4-hydroxytamoxifen (4-OHT) to be performed by [name] using LC/MS/MS as published by us previously[16, 17]. Blood will be collected with anticoagulant K2-EDTA.
- 3. Plasma hormone levels for steroid hormones: estradiol, progesterone, dehydroepiandrosterone (DHEA), androstenedione and testosterone to be measured by LC/MS/MS using methods developed for prior studies by our group[45]. Blood will be collected with anticoagulant K2-EDTA.
- 4. *Plasma concentrations of IGF-1/IGFBP-3 and SHBG*: IGF-1 and its binding proteins IGFBP-3, and SHBG[16, 46] to be measured by ELISA assays at Northwestern University, Comprehensive Metabolic Core. Blood will be collected with anticoagulant K2-EDTA.
- 5. Plasma levels of coagulation cascade proteins: four blood coagulation protein assays [factor VIII, factor IX, von Willebrand factor (vWF), and Protein S] using plasma samples to be performed at Hemostasis Laboratory, Northwestern Memorial Hospital. Blood will be collected with anticoagulant citrate.

Table 2. Priority list of Biomarker analysis (FFPE tissue block , 15 sections, 4 micron each)				
1	1 H&E section for histology review (leading)			
2	2 sections for Ki67 IHC assay (including an extra for repeats)			
3	1 section for Progesterone Receptor IHC assay			
4	1 section for Estrogen Receptor IHC assay			
4	9 sections for macro-dissection and RNA extraction			
5	1 H&E section for histology review (trailing)			

lymph node, if available.

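### Does section 13.5 need a formal comparison of gel and oral endoxifen levels, because the hypotheses claim one and a cross-reference hints at a test against zero?

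*Combined protocol and SAP*

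**What the plan says.** **Plasma.** Objective 1.2.2 is to measure plasma levels of the (E) and (Z) isomers at each dose. Hypothesis 2 in 2.3.1 goes further: plasma endoxifen (ENX) at each dose "will be significantly lower than those seen in women on oral tamoxifen". Section 13.5(2) says that the levels "will be reported as observed concentrations with appropriate CIs". It cites no oral value and plans no test. The only oral plasma figure, 6 ng/mL (16 nM), is in the background (2.2).

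**The cross-reference.** Items 3-5 of 13.5 cover plasma steroid hormones, estrogenic response proteins and coagulation parameters. They promise a 95% CI for the mean post-minus-pre difference, and "a test of the central parameter = 0 will be provided as in the previous objective". Item 2 has neither a difference nor a test. Section 3.7 places the drug assays at one time point: "Examination of breast tissue and plasma samples for drug concentration (at the end of intervention").

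**Tissue.** Hypothesis 1 in 2.3.1 says that tissue ENX "will reach the concentrations achieved in our prior study of oral tamoxifen versus 4-OHT gel (5.8 ng/g tissue"). Section 8.2 states the endpoint as: "Demonstrate dermal permeation of ENX gel is similar to ENX levels achieved with oral delivery (mean values of 5-6 ng/G breast tissue"). Section 2.2 adds that the dose, "given the expected high mammary concentrations, could potentially be lowered", and reports a median of 8 ng/g in mammary adipose tissue on oral tamoxifen. The analysis in 13.5(1) is: "Comparison of breast tissue concentrations of ENX at each dose will be done using visualization, graphics", with a confidence interval.

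**The concern.** Low systemic exposure is one of the stated reasons for treating through the skin (2.1), and hypothesis 2 is where the plan turns it into a claim of significance. If 13.5 schedules no comparison with oral tamoxifen, that claim has no planned answer.

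The back-reference could make matters worse. If a test against zero were run on plasma ENX, it would show only that drug is present. With all 8 women above zero the exact signed-rank p is 0.0078, whatever the concentration.

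For tissue, *reach* points in one direction and *similar* in both. A level well above the oral one would meet the first and contradict the second, and 2.2 does expect high levels. The same data could then be written up as a success or a failure. The assays separate the isomers, but 13.5(1)-(2) do not say whether a comparison would use (Z), (E) or total ENX.

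**Working it through.** The documents give no power, margin or threshold for a comparison with oral levels, so there is no design figure to reproduce. One side check agrees: 6 ng/mL divided by 373.49 g/mol (Appendix G) is 16.06 nM, against the stated 16 nM.

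**1. Where does the test against zero belong?** The sentence opens by naming hormones, response proteins and coagulation parameters, and its estimate is a post-minus-pre difference. Under 7.2.1 and 7.4.2 blood for these markers is drawn at screening and on the day of surgery, so the difference exists for them. Drug is assayed only at the end of treatment, so no difference exists for it. Item 6 of 13.5 describes the same analysis in full for the tissue markers (CI of the mean difference, nonparametric test of zero). An analyst would apply that to items 3-5 and nothing of the kind to item 2. The signed-rank p-values (2/2^8 = 0.0078 for 8 women, 2/2^16 = 0.00003 for 16) describe an analysis that the plan does not schedule.

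**2. What would a formal plasma comparison add?** Inputs: 8 women at 20 mg; 8 at 10 mg in Cohort 1 and 8 in Cohort 3, so 16 at 10 mg if pooled, which 13.5 does not say; oral value 6 ng/mL, taken as fixed. The documents give no between-woman CV, so 50% and 100% are assumed.

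- Log-scale SD = sqrt(ln(1 + CV²)): 0.472 and 0.833.
- CI factor = exp(t(0.975, n-1) × SD/√n), with t = 2.365 (n = 8) and 2.131 (n = 16): 1.484 and 2.006 for n = 8; 1.286 and 1.558 for n = 16.
- The upper 95% limit of the geometric mean is below 6 when the estimate is below 6/factor: 4.04 and 2.99 ng/mL (n = 8); 4.66 and 3.85 (n = 16).
- The chance of that is P(noncentral t > t(0.975, n-1)), with noncentrality -ln(ratio) × √n/SD.

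| True gel/oral ratio | n = 8, CV 50% / 100% | n = 16, CV 50% / 100% |
|---|---|---|
| 0.60 (rat plasma in 2.2: 1.8/3) | 0.747 / 0.323 | 0.981 / 0.631 |
| 0.20 (five-fold lower, 6.2, 4-OHT gel) | over 0.99 / 0.996 | over 0.99 / over 0.99 |

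If the gel level is five-fold lower, the interval in 13.5(2) will show it plainly without a rule. If the ratio is near 0.60, a rule at n = 8 may well be inconclusive, and the interval will show that too. The 0.60 is a loose guide. In 2.2 the rat oral dose corresponds to 28.8 mg/day in a woman, not 20 mg, and the rat gel (over 97% (Z)) corresponds to 10 mg/day. The 10 mg human gel contains 5 mg of (Z) (section 2.2).

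**3. When would the two tissue verbs diverge?** The whole 95% CI of the geometric mean lies above 6 ng/g when the estimate exceeds 6 × factor: 8.91 and 12.03 (n = 8); 7.72 and 9.35 (n = 16). These set a geometric mean against a figure that 8.2 gives as a mean. If that is an arithmetic mean of log-normal values, the matching geometric mean is 6/√(1 + CV²) = 5.37 and 4.24. The thresholds become 5.37 × 1.484 = 7.97 and 4.24 × 2.006 = 8.51 (n = 8), and 6.90 and 6.61 (n = 16). The divergence point therefore depends on a statistic that the documents do not identify, and no rule in the plan uses it.

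**4. Isomers.** Separate (E) and (Z) measurement is set out in 1.2.1, 1.2.2, 8.2 item 2 and 9.1. The isomer behind the oral values is not stated, so the effect of that choice cannot be sized.

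**The case for a change.** The strongest case for a change is that it costs only wording. *Significantly* in 2.3.1 and *Demonstrate* in 8.2 promise more than 13.5 delivers. A reader may compare the interval with 6 ng/mL, but the plan does not say that this will be done, or on which isomer or statistic. Items 3-5 name no test, since only item 6 says nonparametric. The oral tissue benchmark appears as 5.8, as 5-6 (mean) and as 8 ng/g (median, adipose), and 2.3.1 does not say which arm the 5.8 comes from; that it is the oral arm is inferred from 8.2.

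All of this stands as description. It does not show that the planned analysis would mislead. The stronger wording sits in rationale and endpoint text, next to hypotheses phrased as loosely as minimal change, if any. The objectives say *measure*, 13.1 accepts that formal comparison is limited by sample size, and 13.8 sets 95% intervals for measurements of response. The Cohort 3 dose was chosen on skin irritation and on permeation compared between the two doses (3.2.1), not on a comparison with oral levels.

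The firmer remedy, a CI bound against the oral value, has problems of its own. That value is historical, has no stated error and comes from a longer exposure (at least 6 weeks, against 21-28 days here). By 3.2.1, Cohorts 1 and 2 were complete and breast drug levels had been discussed. A bound set now would be post hoc for 16 of the 24 actively treated women, and for all 8 at 20 mg. Statisticians could reasonably differ on whether that improves on a plain interval.

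**Conclusion.** No change to the plan is needed. Following 13.5 as written gives per-dose concentrations with intervals, which is what objectives 1.2.1 and 1.2.2 ask for. An analyst can set them beside 6 ng/mL for plasma and 5-6 ng/g for tissue as a historical, descriptive comparison. What remains is a stale cross-reference, whose intended content is clear from item 6, and hypothesis wording stronger than a small Phase I trial supports. Neither affects the primary endpoint, safety, dosing, data collection or the secondary estimates.

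A formal bound would settle little. Its chance of success is over 99% if plasma levels are five-fold lower than on oral tamoxifen, and 75-32% at n = 8 if the ratio is 0.60. These figures assume log-normal values, a CV of 50-100% and a fixed oral value of 6 ng/mL; the ratios are scenarios, not predictions. The conclusion does not depend on them. It rests on reading the test in items 3-5 as belonging to the post-minus-pre markers, and on the absence of any margin or decision tied to the oral level.
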